**13.0 Potential Risks to Study Subjects and Risk Mitigation**

Expected risks to subjects in this study include all those currently associated with osteoarthritis and as sequela to microfracture surgery. Additional risk to subjects which might arise as the result of study participation are discussed below.

**13.1 Risk of Losartan Administration**

A full description of expected side effects can be found in Losartan's directions for use <https://www.bioportfolio.com/resources/drug/15151/Losartan-Potassium-Sandoz-Inc.html>

Known side effects include dizziness, headache, diarrhea, stomach pain, muscle cramps, leg or back pain, insomnia, tiredness and cold or flu symptoms such as stuffy nose, sneezing, sore throat, fever and cough. In addition, there is a chance that administration of losartan will not improve the outcomes of microfracture.

Subjects will be fully informed about expected side effects of losartan and will be instructed to inform the Primary Investigator should these symptoms become apparent. Informed consent will include information revealing that it is unknown if losartan will improve the outcomes of microfracture.

**13.2 Risk of Placebo Administration**

If results of this study reveal that administration of losartan improves the results of microfracture, subjects randomized to placebo may miss these benefit(s).

Subjects will be fully informed regarding the expected outcomes of standard microfracture surgery and will be told that they have only a 50% chance of being randomized to receive losartan. In addition, subjects will be told that the advantages of receiving losartan following microfracture are unknown.

**13.3 Risks Associated With MRI**

The MRI scan involves exposure to loud noise, and positioning in a small space. Subjects may feel claustrophobic, fatigued or nauseated especially if they are uncomfortable with tight spaces. The MRI scan does not involve the use of x-rays or injectable dyes. There are no known reports of increased cancer or birth defects associated with this procedure. The MRI scan exposes the subject to high magnetic fields, which can be dangerous for those with pacemakers and some metal implants.

All participants will be offered music and/or earplugs to reduce the noise level produced by the MRI machine. Participants with a pacemaker, hearing aid, aneurysm clips or artificial heart valves, and other forms of loose metal implants will be excluded from the study as assessed by

---

**Clinical Protocol No. 2019-15**

**Version 001**

**Page 31 of 58**

a pre-MRI questionnaire administered as part of the eligibility screening prior to enrollment. The screening will be conducted again the day of the MRI, to ensure the participant can still safely undergo an MRI. It is possible that a participant will become unexpectedly ineligible for an MRI between the first and second testing days (e.g. if they receive a pacemaker after the first testing day). In this case, the participant will be allowed to continue with motion capture and DSX testing but will not have an MRI taken.

#### **13.4 Risks Associated with PRO Questionnaires:**

Completion of the PRO questionnaires should take each subject approximately 20-30 minutes. There is a risk that subjects may find this laborious and experience emotional distress.

To mitigate this experience, subjects will be fully informed and instructed on how to complete each questionnaire. Subjects can also elect to taking “breaks” during questionnaire completion. Subject will also be offered the option of completing questionnaires electronically at home.

#### **13.5 Breach of Confidentiality**

There is a possibility that personal information could be accidentally or inappropriately breached during this research.

The Steadman Clinic and Steadman Philippon Research Institute use many physical, technologic and administrative measures to protect your information. Deidentifying study information, assignment of an alpha-numeric study identifier, locking offices and cabinets, password-locked work stations and encryption protect electronic information. Information will be used and analyzed in a manner that does not contain any of identifiable information. When results of this research are presented at scientific meetings and in medical journals, all information that can possibly identify subjects will be removed.

All electronic PRO data is encrypted using the AES-256 encryption algorithm, and high-grade SHA-256 RSA encryption is used for https connections over TLS. Secure network access is enforced by multi-tiered firewalls, custom system configurations and multi-zones networks.

---

## **14.0 Stopping Rules/Termination of Study Enrollment**

The triggering of stopping rules will result in prompt discontinuation of subject enrollment and notification of the Medical Monitor and IRBs. Although enrollment will cease, all subjects enrolled up until that point will continue to be followed according to the protocol for evaluation for duration of the clinical trial. Enrollment will be reconvened only when permission is granted by the IRB.

### **14.1 Termination of Enrollment by the Principal Investigator**

The Principal Investigator may terminate study enrollment at any time for any of the following reasons.

1. Any unexpected serious or life-threatening AE that cannot be determined to be unrelated to Study Medication;
2. It is determined that the protocol precipitates multiple subject non-compliance issues beyond reasonably missed follow-up.

### **14.2 Termination of Enrollment by the Medical Monitor**

The Medical Monitor may terminate enrollment due to the emergence of significant safety signals.

### **14.3 Removal of Subjects from the Study**

Principal Investigators may remove a subject from the study if:

1. Subject demonstrates poor compliance with study protocol;
2. There is concurrent illness or required medical treatment that interferes with study assessments;
3. The Principal Investigator determines that the subject's health, safety or welfare is at risk.

For subjects taking losartan, symptomatic hypotension, significant electrolyte imbalance, acute renal failure, or severe nausea or vomiting precluding medication compliance will result in immediate discontinuation of the subject's course of medication.

---

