**6.0      Summary of Proposed Placebo Controlled Trial**

Our objective is to determine in a placebo controlled if the administration of losartan post microfracture will result in reduced fibrosis in healing tissue and will improve hyaline cartilage repair. Patients who have undergone microfracture for a focal chondral defect of the femoral head or acetabulum will be considered candidates for enrollment. A member of the Study Team will review the patients' record to determine if all inclusion/exclusion criteria are met. Each potential subject will be fully informed regarding all aspects of the proposed study and will be required to review and sign a full, IRB approved, informed consent document attached as [Appendix A.](#)

Forty patients who have consented to participate will be assigned, 1:1 via block randomization, one of the two blinded study groups.

- 1) n=20: standard microfracture + losartan [TGF- $\beta$ 1 blocker]); or
- 2) n=20 standard microfracture + placebo.

Losartan and the inactive placebo are collectively referred to as Study Medication.

A Study Team member will then inform the pharmacist of the patient's assigned group and the patient will pick up study medication prior to leaving the hospital following microfracture. This is expected to occur on post-operative day one (POD1). Subjects will self-medicate for one month following surgery either 12.5mg losartan twice daily or placebo twice daily. A log recording medication administration (Medication Log) will be maintained daily by the subject during the administration month.

Subjects will also be given a blood pressure cuff to take home to for twice daily self-monitoring and recording of blood pressure while the Study Medication is being administered, after which time blood pressure should be measured once weekly until the 3-month visit.

Subjects will be instructed to undergo physical therapy and a document describing the recommended content of that therapy will be provided.

At 7-10 days postoperatively subjects will be required to undergo a standard Basic Metabolic Panel. Results will be faxed to the Principal Investigator or designee. Subjects will also be interviewed by telephone by a Study Team member to document possible protocol violations, all adverse events, subject blood pressure and compliance with blood draw and study medication.

---

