### **11.4 Telephone Contact by Study Team Post-operative day 30- (No Visit Required) (approximately one month)**

Study Medication is expected to be completed at this time. A Study Team member will contact each subject to confirm that the Study Medication has been completed and logged. Subjects will be asked to send to the Study Team, a copy of the Study Medication Log. The occurrence of protocol deviations and all adverse events will be recorded.

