**11.8 Visit 3: 18 Months Post-operative (+/- 8 weeks)**

All procedures performed in Visit 3 will be repeated. In addition, subjects will undergo a Morphological and quantitative T2 MRI to be performed at Steadman Research Institute according to a specific and consistent imaging protocol. Adverse events related to the target hip and protocol deviations will be recorded.

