**15.0 Statistical Considerations**

Patients will be randomized with a 1:1 allocation ratio into either the microfracture plus losartan versus microfracture alone group. Block randomization will be used with block sized of n=8 to ensure that groups are of approximately equal size at study completion, even if some patients are lost to follow-up or unenrolled.

Intent-to-treat analysis will be performed. We will compare group means, with the hypothesis that greater post-operative PROs and higher graft quality as assessed with quantitative imaging will be observed in the microfracture plus losartan group compared to microfracture alone. Analysis of Covariance (ANCOVA) or Linear mixed-effect models with random intercepts will be used to compare groups while adjusting for the baseline measurement of each subject.

The effect size of microfracture plus losartan compared to microfracture alone with respect to patient reported outcomes is unknown, so a sample size calculation was performed based on anticipated quantitative

Anticipated effect sizes for the group difference with respect to MRI-assessed cartilage quality were derived from the literature, however a paucity of helpful literature was found in the hip literature. Sample size for this study was determined via a statistical power analysis using published data from Apprich, et al , who compared patients treated with microfracture of the talus versus patients treated with matrix-associated autologous chondrocyte transplantation (MACT).

The primary outcome metric reported in Apprich, et al was a semi-quantitative scale of diffusion-weighted imaging (DWI) acquired by MRI and the paired differences between DWI of the repaired tissue and healthy reference cartilage for each patient was reported for each treatment group. We aim to power this study to detect an effect size between the microfracture alone and microfracture plus losartan groups that is equal to the observed between-group effect size calculated from Apprich, et al (d=1.107).

The significance level will be set at  $\alpha=0.05$ . Assuming 2-tailed testing and requiring 90% statistical power, 19 patients per group are sufficient to detect the effect size of interest. We aim to enroll 20 subjects per group. Power calculations were performed using G\*Power (version 3.1; Universität Düsseldorf).

---

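### Section 14.3 allows removal from the study for poor compliance, and nothing provides for the 18-month MRI afterwards, which weakens the intent-to-treat MRI comparison by a probably small amount

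*Combined protocol and SAP*

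**What the plan says.** Section 14.3 lists three grounds on which the Principal Investigator may remove a subject from the study. The first is "Subject demonstrates poor compliance with study protocol", with no definition or threshold. The last paragraph of 14.3 is a different rule: for named clinical events it ends the course of medication only.

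Randomisation follows consent at Visit 1 (11.1, Appendix B), so any later removal is of a randomised subject. The telephone interview at days 7-10 covers "compliance with blood draw and study medication" (6.0). At about day 30 to 35, "A Study Team member will contact each subject to confirm that the Study Medication has been completed and logged" (11.4; the Synopsis and Appendix B give day 35). The MRI outcome comes much later: at the 18-month visit "subjects will undergo a Morphological and quantitative T2 MRI to be performed at Steadman Research Institute" (11.8). Appendix B marks T2 MRI only at screening and at 18 months.

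Section 15.0 says "Intent-to-treat analysis will be performed" and "Analysis of Covariance (ANCOVA) or Linear mixed-effect models with random intercepts will be used to compare groups", adjusting for baseline. It chooses the block size so that the groups stay similar in size "even if some patients are lost to follow-up or unenrolled". It gives no rule for a missing MRI.

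Two sections touch on continued follow-up. Section 14.0 says "Although enrollment will cease, all subjects enrolled up until that point will continue to be followed according to the protocol", which concerns a halt in enrolment. Section 20.1 covers missed visits and voluntary withdrawal. Neither addresses a subject removed under 14.3.

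**The concern.** Compliance is observed after randomisation and may depend on tolerance of the study medication or on recovery. If subjects leave the MRI comparison because of it, the comparison is between those retained rather than between the groups as randomised. Block randomisation balances numbers at allocation; it does not control who leaves later. With 20 per arm, each lost subject is 5% of an arm, and an outcome that was never collected cannot be recovered at analysis.

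Patient-reported outcomes are less exposed. They are collected from 3 months on, and under the mixed model any post-operative values obtained before removal stay in the analysis.

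**Working it through.** **What a removed subject contributes.** Both models in 15.0 adjust for baseline, and there is a single post-operative MRI. A subject without that scan has a covariate but no outcome, and so adds nothing to the group comparison under either model. Imputation, or a longitudinal model with baseline treated as an outcome, would change this. The plan specifies neither.

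**The plan's own figure.** Inputs from 15.0: d = 1.107, two-sided alpha 0.05, power 90%, 1:1 allocation. For a two-sample t-test, power = P(|T| > t_crit), where T is noncentral t with n1 + n2 - 2 degrees of freedom and noncentrality d x sqrt(n1 n2/(n1 + n2)).

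- 18 v 18: noncentrality 1.107 x sqrt(9) = 3.321, power 0.897.
- 19 v 19: noncentrality 1.107 x sqrt(9.5) = 3.412, power 0.913.

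So 19 per group is the smallest size that reaches 90%, as the protocol states.

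**Power after losses, same formula.**

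| Evaluable | Lost of 40 | Power |
|---|---|---|
| 20 v 20 | 0 | 0.927 |
| 20 v 19 | 1 | 0.920 |
| 19 v 19 | 2 | 0.913 |
| 19 v 18 | 3 | 0.905 |
| 20 v 17 | 3 | 0.904 |
| 18 v 18 | 4 | 0.897 |
| 19 v 17 | 4 | 0.896 |
| 20 v 16 | 4 | 0.894 |
| 18 v 16 | 6 | 0.878 |

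**Bias and false-positive rate.** The documents give no removal rate, so these inputs are assumptions: 2 to 4 removals in one arm and 0 to 2 in the other, with removed subjects 0.5 to 1.0 SD worse than those kept. If k of 20 are removed and differ from those kept by g SD, the mean of those kept differs from the whole-arm mean by k x g/20. The bias in the comparison is therefore (k_A g_A - k_B g_B)/20. The null rejection rate is the power formula above with d set to that bias. No baseline adjustment is used.

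| Removed | Gap (SD) | Bias (SD) | Null rejection |
|---|---|---|---|
| 2 v 2 | equal in both arms | 0 | 0.050 |
| 3 v 1 | 0.5 | (3 - 1) x 0.5/20 = 0.05 | 0.052 |
| 3 v 1 | 1.0 | 2 x 1.0/20 = 0.10 | 0.060 |
| 4 v 2 | 0.5 | 0.05 | 0.052 |
| 4 v 2 | 1.0 | 0.10 | 0.059 |
| 2 v 2 | 1.0 in one arm, 0 in the other | 2 x 1.0/20 = 0.10 | 0.060 |
| 4 v 0 | 1.0 | 4 x 1.0/20 = 0.20 | 0.089 |

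The sixth row shows that equal numbers remove the bias only if the gap is also equal. The last row is an extreme case.

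**The case against.** The case against treating this as a serious defect is strong in several respects.

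- **Removal is discretionary.** Section 14.3 says may, and nothing forbids an 18-month scan after removal. A reader might infer that removed subjects cannot be included and that intent-to-treat is therefore contradicted. The documents do not go that far: they are silent on follow-up after removal.
- **Missed tablets are not tied to removal.** The telephone contacts confirm compliance and record deviations. Section 20.2 has deviations recorded through the end of study medication and assessed for subject risk and data integrity. A reader might infer that a poor medication log leads to removal; no section says so. Poor compliance may also mean non-attendance, and then follow-up wording will not produce a scan.
- **Adverse events are not simply lost.** Section 12.2 requires all adverse events to be followed to resolution or a stable endpoint, and repeats this for adverse reactions and suspected reactions. Only new target-hip events after removal are at risk of being missed.
- **The investigator is blinded (6.1).** That makes a strong imbalance such as 4 v 0 unlikely, so the 8.9% rejection rate should not be read as an expected result.
- **The study is exploratory.** Section 5.1 says it is not meant to support a labelling change.
- **The consent appendix was not available.** It might contain terms on follow-up after removal.

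These points limit the size of the concern and the certainty with which it can be stated. They do not remove it. Section 14.3 separates leaving the study from stopping medication and places poor compliance under leaving the study. Blinding prevents removal on known allocation, but not removal on a consequence of allocation. Section 15.0 still has no rule for a missing MRI.

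**Conclusion.** The point holds as a gap in provision. A randomised subject can be removed from the study for poor compliance, no available section provides for the 18-month MRI afterwards, and 15.0 does not say what happens without it. This weakens the stated intent-to-treat analysis of the MRI endpoint but does not invalidate it.

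The likely effect is small and its actual size is unknown. On the assumed inputs with removals in both arms, the bias is 0 to 0.10 SD against a planned 1.107 SD, and null rejection is 5.0% to 6.0%. Power stays above 0.90 with up to three losses and is 0.894 to 0.897 with four, so a reading that the trial would be seriously underpowered is not supported. If removals are few and unrelated to outcome, or balanced with similar outcome gaps in the two arms, there is little or no bias. Severity is minor; this is a cheap improvement.

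**What to change.** **In 14.3**, state that poor compliance, including with study medication, does not by itself end follow-up. Such subjects are still asked for the scheduled 18-month MRI, the patient-reported outcomes and target-hip adverse event follow-up, unless:

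- consent is withdrawn;
- MRI is not possible or would not be interpretable, including where the second ground in 14.3 applies (illness or treatment that interferes with assessments); or
- the investigator judges continued assessment to be a risk to the subject.

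The clinical grounds for stopping medication stay unchanged.

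**In 15.0**, state that no subject with an outcome is excluded for non-compliance. Report removals and missing MRIs by arm with reasons. Pre-specify one simple sensitivity analysis for missing 18-month MRI values, for example imputation from baseline and arm followed by one stated unfavourable shift of the imputed values. As a guide to scale, one value in 20 shifted by 1 SD moves the group difference by 1/20 = 0.05 SD.

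**Cost:** a wording amendment and some staff effort to retain a few subjects through visits and contacts already scheduled, with no new assessments. The follow-up wording gains little for subjects who refuse to attend; for them only the reporting and the sensitivity analysis help.

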## **6.1 Blinding**

All study subjects and Study Team members responsible for subject evaluation, data management and analysis (Including the Principal Investigator) will be blinded to treatment through 18 months follow-up. In addition, any individuals engaged by the Principal Investigator to provide of radiographic, laboratory testing and and/or verification of data will be blinded to treatment.

One Study Team Member responsible for group assignment, the pharmacist responsible for medication distribution and the Independent Medical Monitor will be unblinded.

---

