## **12.6 Reporting of Adverse Events**

### **12.6.1 Appointment of a Non-Blinded Medical Monitor and FDA**

An Independent Medical Monitor will be selected to oversee study safety.. This individual is to be an appropriately certified physician experienced in the management of blood pressure.. He/she will be unblinded to Study Medication.

The portion of this study which is greater than minimal risk involves administration of losartan or placebo for 1 month following enrollment in the study. All adverse events will be monitored by the blinded Study Team during this time period.

The Principal Investigator will be responsible for confirming the severity of all adverse events. All serious and unexpected adverse events will be reported to the unblinded Independent Medical Monitor within 24 hours of their disclosure to the Principal Investigator. The Medical Monitor will review data or events reported by the Study Team within 72 hours of disclosure to the Medical Monitor.

During this time appropriate care will be given to the study subject. If managing adverse events requires unblinding to the any member of the Study Team, the appropriate team member will disclose the group identity to the necessary medical provider.

The IRB will be notified of unanticipated and serious adverse events within 5 business days of identification. This reporting may come from the Study Team, the Independent Medical Monitor, or both.

If a subject experiences a serious and unexpected adverse event while taking losartan, FDA will be notified by telephone or facsimile within 7 days, and in writing within 15 days hours (after the Principal Investigator's initial receipt of the information).

Each written notification may be submitted on FDA Form 3500 or in a narrative format and shall bear prominent identification of its contents, i.e., "Med Watch Safety Report".

---

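### Section 14.3 limits a mandatory medication stop to the losartan arm, so the blinded team cannot tell whether it applies to a given subject

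*Combined protocol and SAP*

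**What the plan says.** The last paragraph of Section 14.3 orders a stop to medication: "For subjects taking losartan, symptomatic hypotension, significant electrolyte imbalance, acute renal failure, or severe nausea or vomiting precluding medication compliance will result in immediate discontinuation". It states no equivalent rule for placebo subjects and does not say who carries out the stop.

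The protocol has a term that covers both arms. Section 6.0 states: "Losartan and the inactive placebo are collectively referred to as Study Medication". Section 14.1, in the same chapter, uses it for its own safety trigger, an event that "cannot be determined to be unrelated to Study Medication".

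Section 6.1 keeps subjects, evaluating staff and the Principal Investigator blinded until 18 months. It then lists the exceptions: "One Study Team Member responsible for group assignment, the pharmacist responsible for medication distribution and the Independent Medical Monitor will be unblinded". On safety during the dosing month, Section 12.6.1 says: "All adverse events will be monitored by the blinded Study Team during this time period". It adds: "The Principal Investigator will be responsible for confirming the severity of all adverse events".

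**The concern.** A stop rule that must act at once should rest on facts that the people applying it hold. Here it rests on the allocation, which they are meant not to know.

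Two things are at stake. The first is blinding. If the rule is followed literally, a stop after a listed event points to losartan, and continued dosing after one points to placebo. That hint can reach the Principal Investigator while he or she is still grading severity (Section 12.6.1) and judging relationship to the medication (Section 12.2). The second is prompt action. A team that reads the rule literally has to find out the arm before it knows whether the stop is compulsory.

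**Working it through.** No figure in the plan is at issue, and the sample size and significance level are untouched. The check is mainly a reading of sections against each other, followed by an illustration of size.

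**1. Whom the rule covers.** Current losartan use is an exclusion (Section 10.3.2, item 3). The condition in 14.3 can therefore only mean subjects randomized to losartan.

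**2. Who sees the trigger.** Symptoms reach the blinded Study Team (Section 12.6.1). Metabolic panel results, which would show an electrolyte or creatinine problem, go to the Principal Investigator or a designee (Section 6.0). The Principal Investigator is blinded (Section 6.1).

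**3. Whether another route supplies the stop blind.**
- Section 14.3, item 3, lets the investigator remove a subject whose safety is at risk, in either arm. It is discretionary, and it is removal from the study rather than a medication stop.
- Section 12.6.1 allows group identity to be disclosed when managing an event requires it. That is a look-up of the arm.
- The unblinded Medical Monitor is told of serious and unexpected events within 24 hours and reviews within 72. Section 12.5 limits serious events to fatal or life-threatening ones. If both conditions are required, many listed events never reach the monitor. If either is enough, the route is still not immediate.
- Section 16.0 gives the investigator control of the Study Medication. This does allow a blinded stop in anyone, but 14.3 does not call for it.

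**4. Size of the hint, as an illustration.** Take 1:1 allocation (Section 15.0). Let r be the ratio of listed events, losartan to placebo, and q the share of placebo subjects with a listed event who are stopped by discretion. The documents give neither; both are assumptions. If every losartan subject with a listed event is stopped,

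P(losartan | stopped) = r / (r + q).

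Arm-neutral wording corresponds to q = 1.

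| r | q = 0 (literal, no discretionary stops) | q = 0.5 | q = 1 (neutral) | Added at q = 0 | Added at q = 0.5 |
|---|---|---|---|---|---|
| 1 | 1/1 = 1.00 | 1/1.5 = 0.667 | 1/2 = 0.500 | 0.500 | 0.167 |
| 2 | 2/2 = 1.00 | 2/2.5 = 0.800 | 2/3 = 0.667 | 0.333 | 0.133 |
| 5 | 5/5 = 1.00 | 5/5.5 = 0.909 | 5/6 = 0.833 | 0.167 | 0.076 |

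At q = 1 the wording adds nothing. The q = 1 column is the hint that comes from the event itself, and rewording would not remove it. The value of 1.00 also requires that an observer knows no placebo subject is ever stopped.

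**5. How many subjects.** The documents give no expected count. Section 5.3 reports no significant effects in normotensive subjects at 12.5 mg, and Section 10.3.2 excludes hypotensive patients and those on interacting drugs, so few are likely. Each one is 1/20 = 5% of an arm and 1/40 = 2.5% of the trial. These are the weights of one subject, not effects.

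**The case against.** A reader might infer that the blinded team cannot operate the rule at all without the allocation. The documents do not support that. Stopping the tablet in every subject with a listed event satisfies 14.3 for everyone on losartan, and nothing in the protocol text forbids stopping placebo. Section 14.3 sets a minimum for one arm and does not order placebo subjects to continue. The arm has to be known only to decide whether a stop is compulsory, not to carry one out. This part of the objection stands, and it limits the point to the form given here.

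It can also be said that the rule names no actor, that three roles are unblinded, and that Section 12.6.1 uses losartan-specific wording for notifying the FDA, so an arm-specific stop might be intended for an unblinded person. The protocol does not assign the stop to any of those roles, and it gives no reason for treating the arms differently. Section 12.6.1 also requires care while an event is under review ("During this time appropriate care will be given to the study subject"), which makes neglect of a subject unlikely but does not say when the tablet must stop.

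The consent appendix was not available for this review and could tell all subjects when to stop. The point therefore concerns the protocol text only. Finally, the probabilities rest on assumed inputs and run from no added hint to a large one. That is fair: they show the mechanism and its limits, and are not evidence of an actual effect.

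**Conclusion.** The point holds as a minor drafting defect. Section 14.3 makes a mandatory, immediate stop depend on the arm, and the blinded team can apply it blind only by doing more than it says. If they do so in every case, the wording adds no hint about allocation. If they follow it literally, it adds up to 0.50 per stopped subject when listed events are equally common in the two arms, and less when they are commoner on losartan. The number of such subjects cannot be estimated from the documents and is probably small.

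Two stronger conclusions are tempting and should not be drawn. One is that the safety endpoint is biased. That endpoint is the occurrence of adverse events (Section 9.4), and Section 12.2 requires every event to be recorded whatever its severity or presumed cause, so the triggering event is still counted. Severity and causality, where a hint could act, are not listed endpoints. Those engaged for radiographic work are blinded (Section 6.1), and the analysis is by intention to treat (Section 15.0). The other is that subjects are likely to miss a needed stop. The investigator's discretion and the disclosure route make that unlikely.

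Confidence is high for the wording conflict. It is low for any practical effect on blinding.

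**What to change.** Change the opening condition of the last paragraph of Section 14.3 so that it refers to subjects taking Study Medication. The blinded investigator then applies the same criteria at once in both arms, with follow-up continuing, and the allocation is disclosed only if care requires it under Section 12.6.1. The clinical criteria themselves are for the sponsor to decide.

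The cost is one phrase in a protocol amendment, using a term already defined. The downside is that some placebo subjects will stop an inactive tablet. The event itself may still suggest the arm, which no wording can prevent.
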